1.10 Early Stopping, Data Monitoring, and Interim Analysis

This study has accommodation for one or more interim analyses. If an interim analysis is done, a separate interim analysis plan will include details of the planned analyses, disclosure, and plans to protect the integrity of the ongoing study.

Interim analysis may or may not be done for business purposes in any portion of this protocol.

1.11 Modifications from the Statistical Section of the Protocol

This SAP is consistent with the protocol with the following exceptions:

- The primary analysis is characterized more completely with change based on blinded evaluations and communications with key opinion leaders. Modifications of the statistical analysis that represent departures from the protocol are permitted in an adaptive study, and such changes are explicitly allowed in the protocol.
- A conditional sequence of hypothesis tests has been modified to reflect blinded evaluations and communications with key opinion leaders.

Any other modifications will be documented in amendments to the SAP or the clinical study report.

2 Statistical Hypotheses

The primary objective is to show superiority (using a 2-sided test) of TTP399 to placebo at 12 weeks in patients treated with insulin on a dichotomous variable to delineate patients treated with insulin plus placebo from patients treated with modified insulin with TTP399 added followed by a non-inferiority evaluation of change in HbA1c followed by a superiority evaluation of change in HbA1c .

It is noted that the insulin optimization is applied to all subjects who are not already optimized in the opinion of the investigator. After the start of double-blind study medication, intensive medical monitoring results in modifications of insulin for all patients. Under the alternative hypothesis of treatment benefit, the modification of insulin for subjects on active treatment may be altered as a result of the co-administration of TTP399. Modification of insulin for subjects on placebo is considered standard of care. It is concluded, therefore, that the placebo added to insulin standard of care is the control group for treatment with TTP399 added to a modified regimen of insulin.

The statistical evaluation including non-inferiority evaluation and hypotheses to be tested in Part 2 are as follows:

First Compound Statistical Evaluation (full alpha):

The first evaluation is non-inferiority of treatment with TTP399 800 mg daily plus a modified regimen of insulin and treatment with optimized insulin as determined by the insulin-optimization period of the study, if needed, per protocol:

- Evaluation 1:**

Noninferiority will be considered to have been established if the 95% confidence interval is completely bounded by the non-inferiority margin of 0.3%, which is specified in the draft guidance: *Guidance for Industry Diabetes Mellitus: Developing Drugs and Therapeutics Biologics for Treatment and Prevention* (CDER; February 2008), Section V.G.1, “Typically we accept a noninferiority margin of 0.3 or 0.4 HbA1c percentage units provided this is no greater than a suitably conservative

estimate of the magnitude of the treatment effect of the active control in previous placebo-controlled trials.”

- The 95% confidence interval will be constructed for the difference between the two treatment groups in mean change in HbA1c to Week 12 using the ANCOVA model as described in the statistical methodology section.
- If the 95% confidence interval is entirely bounded by 0.3% (where a difference of 0.3% reflects the placebo mean is 0.3% better than the mean of the patients treated with TTP399), then the statistical conclusion will follow that treatment with 800 mg TTP399 combined with a modified regimen of insulin is non-inferior to placebo added to insulin following the usual standard of care.

Conditional on the statistical conclusion of non-inferiority of TTP399 relative to placebo, statistical evaluation continued.

It is noted that noninferiority relative to change from baseline in insulin is planned using the confidence interval approach to demonstrate that the maintenance of control of HbA1c achieved during the insulin-optimization period is not driven by an increase in insulin among subjects treated with TTP399. Formal evaluation of this aspect of non-inferiority is not planned, so the statistical evaluation is considered to be nominal rather than rigorous.

The Hochberg method is used for alpha control for Evaluation 2 and Evaluation 3.

- **Evaluation 2:**

Superiority on HbA1c is evaluated:

- H_{01} : The change from baseline in HbA1c at Week 12 for the group treated with 800 mg TTP399 is equal to that of the placebo group.
- H_{11} : The change from baseline in HbA1c at Week 12 for the group treated with 800 mg TTP399 is not equal to that of the placebo group.

- **Evaluation 3:**

It is noted that strict application of the Hochberg methodology implies that rigorous p-values may not be applicable in the event of failure to reject either hypothesis in Evaluation 2. The intersection hypothesis is, however, applicable, and it is the intention of this analysis plan to continue testing under the intersection hypothesis and interpret p-values as rigorous as opposed to nominal.

Superiority on treatment response is evaluated:

- H_{02} : The proportion of treatment responders at Week 12 for the group treated with 800 mg TTP399 is equal to that of the placebo group.
- H_{12} : The proportion of treatment responders at Week 12 for the group treated with 800 mg TTP399 is not equal to that of the placebo group.

The study is declared to have met its primary endpoint if Evaluation 1 concludes TTP399 plus the modified regimen of insulin is noninferior to optimized insulin

And

Using the Hochberg method, either Evaluation 2 finds TTP399 is superior on HbA1c or Evaluation 3 finds TTP399 is superior on the proportion of treatment responders.

Conditional on achievement of endpoints, statistical evaluation continues.

Conditional Second Statistical Evaluation:

- **Evaluation 4:**

Superiority on daytime time in range is evaluated:

- H_{03} : The mean change in daytime time in range from baseline to Week 12 for the group treated with 800 mg TTP399 is equal to that of the placebo group.
- H_{13} : The mean change in daytime time in range from baseline to Week 12 for the group treated with 800 mg TTP399 is not equal to that of the placebo group.

Conditional Third Statistical Evaluation:

- **Evaluation 5:**

Superiority on time in hypoglycemia using 70 mg/dl as the threshold is evaluated:

- H_{04} : The mean change in time in hypoglycemia using 70 mg/dl as the threshold from baseline to Week 12 for the group treated with 800 mg TTP399 is equal to that of the placebo group.
- H_{14} : The mean change in time in hypoglycemia using 70 mg/dl as the threshold from baseline to Week 12 for the group treated with 800 mg TTP399 is not equal to that of the placebo group.

Conditional Fourth Statistical Evaluation:

- **Evaluation 6:**

Superiority on time in hypoglycemia using 54 mg/dl as the threshold is evaluated:

- H_{05} : The mean change in time in hypoglycemia using 54 mg/dl as the threshold from baseline to Week 12 for the group treated with 800 mg TTP399 is equal to that of the placebo group.
- H_{15} : The mean change in time in hypoglycemia using 54 mg/dl as the threshold from baseline to Week 12 for the group treated with 800 mg TTP399 is not equal to that of the placebo group.

Conditional Fourth Statistical Evaluation:

- **Evaluation 7:**

Superiority on Quality of life Likert scale score is evaluated:

- H_{06} : The mean score for the single-item Likert scale for overall improvement in quality of life at Week 12 for the group treated with 800 mg TTP399 is equal to that of the placebo group.
- H_{16} : The mean score for the single-item Likert scale for overall improvement in quality of life at Week 12 for the group treated with 800 mg TTP399 is not equal to that of the placebo group.

3 Estimand Specification

This SAP is constructed to conform to regulatory guidance. In particular, this section is included as recommended by ICH E9 (R1) Addendum on estimands and sensitivity analysis in clinical trials to the guideline on statistical principles for clinical trials (30 August 2017).

In accordance with ICH E9 Addendum, the specification of the estimand is included in this SAP with the 4 attributes detailed in ICH E9 Addendum, Section A.3.1:

A. The Population, that is, the patients targeted by the scientific question:

For this study, the population consists of subjects with type 1 diabetes who meet eligibility requirements for the study, have qualified through the basal insulin-optimization period (if needed) and the placebo run-in period, receive double-blind medication, and have at least one valid post-baseline measure of HbA1c.

B. The variable (or endpoint) to be obtained for each patient, that is required to address the scientific question:

For this study, the primary endpoint is HbA1c with co-primary importance on treatment responsiveness (whether or not subjects are treatment responders).

C. The specification of how to account for intercurrent events to reflect the scientific question of interest:

For this study, intercurrent events such as blood transfusion or medical treatment with prednisone or major modification in insulin regimen/doses outside the once recommended in the protocol that would render subsequent values as not protocol-meaningful will be set to missing (moved to the SDTM SUPPLB domain to facilitate sensitivity analysis that includes the values) and primary statistical methodologies of multiple imputation will be used to predict what the values were likely to be had the intercurrent event not happened.

- D. The population-level summary for the variable that provides, as required, a basis for a comparison between treatment conditions:

For this study, the population-level summary for the variable is the least-squares mean (LSM) of the treatment difference in mean change from baseline in HbA1c.

4 Populations of Analysis

In accordance with guidance from the International Conference on Harmonisation of Technical Requirements for Registration of Pharmaceuticals for Human Use (ICH) *Statistical Principles for Clinical Trials E9* (1998), the following population of analysis will be used for all statistical analysis:

- The full analysis set (FAS) includes all randomized patients who receive at least one dose of randomized study medication with at least one valid value post-treatment value. The FAS is used for all efficacy analyses.
- The per-protocol set (PPS) includes all FAS patients who do not have significant protocol violations, where a significant protocol violation is one that has the potential to affect analysis conclusions. Final determinations of significant protocol violations will be made at the final blinded data review meeting in accordance with guidance from ICH E9 (Statistical Principles).
- The safety analysis set (SAF) includes all patients who received at least one dose of study medication. The SAF is used for all safety analyses.

In accordance with ICH E9, patients lacking any valid, on-treatment assessment of HbA1c will be excluded from the FAS.

It is noted that the evaluations, reviews, and decisions planned to be made at blind data review meetings are consistent with regulatory guidance as depicted and recommended in ICH E9.

Solely to understand the influence of dropouts on study conclusions, the FAS will be partitioned into completers and dropouts.

Efficacy analysis will be done as randomized. Safety analysis will be done as treated.

PK analyses will be performed using the PK population, comprising those study participants who have received TTP399 and have sufficient PK data for analysis.

5 Specification of the Estimand

In accordance with guidance from the International Conference on Harmonisation of Technical Requirements for Registration of Pharmaceuticals for Human Use (ICH) ICH E9 (R1) Addendum On Estimands and Sensitivity Analysis In Clinical Trials to the Guideline to Statistical Principles for Clinical Trials (2018), the characterization of the estimand includes the following attributes:

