5.1 The Scientific Question of Interest

The scientific question of interest evaluates the potential superiority of TTP399 over placebo in the treatment of T1DM in patients who meet protocol eligibility criteria and do not require concomitant medications, blood transfusions, or other rescue therapies that would influence HbA1c measures (except for insulin), thereby rendering the subsequent values as uninterpretable for protocol-planned purposes.

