5.3 The Variable of Interest

The endpoint or variable of primary interest is change in HbA1c. Additionally, a responder analysis is of keen interest, where a responder is a subject who shows stable or improved HbA1c at endpoint (change is zero or more), no treatment-emergent abnormal value in beta-hydroxybutyrate (BOHB), and no increase in hypoglycemic episodes below 54 mg/ml. Of key interest are parameters associated with glycemic control, including percentage of time in the target range and the coefficient of variation (CV). Important variables of interest from a safety perspective include time in hypoglycemic ranges and occurrence of adverse events of special interest, including severe hypoglycemia and DKA.

5.4 The Specification of How Intercurrent Events Are Reflected in the Scientific Question of Interest

An intercurrent event is any event that occurs after treatment initiation and either precludes observation of the variable or affects its interpretation (ICH E9 addendum, glossary).

Intercurrent events for Part 2 of this study include:

- Blood transfusion.
- Use of concomitant treatments that are known to be associated with impact on HbA1c, specifically use of steroids.
- Shift change in work schedule from day worker to night worker or other life event that may affect HbA1c, such as any situation or major protocol deviation from the usual insulin doses outside of the ones specified in the protocol.

Data from patients during periods of when the InPen or insulin pump fails cannot be interpreted for the protocol-planned purposes. Censored data will invoke statistical methodologies for coping with missingness.

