8.4 Intercurrent Events

This SAP is constructed to conform to regulatory guidance. In particular, this section is included as recommended by ICH E9 (R1) Addendum on estimands and sensitivity analysis in clinical trials to the guideline on statistical principles for clinical trials (30 August 2017).

ICH E9 Addendum defined an intercurrent event as an event that occurs after treatment initiation and either precludes observation of the variable or affects its interpretation.

For this study, intercurrent events such as blood transfusion or medical treatment with prednisone that would render subsequent values as not protocol-meaningful will be set to missing (moved to the SDTM SUPPLB domain to facilitate sensitivity analysis that includes the values) and primary statistical methodologies of multiple imputation will be used to predict what the values were likely to be had the intercurrent event not happened.

It is emphasized that values representing intercurrent events as determined by blind data review (done in accordance with ICH E9 guidance) by medical, clinical, and data management will be flagged as not protocol relevant in the SDTM LB domain, and these values will be moved to the supplementary domain (SUPPLB) of the SDTM dataset; the flag in the LB dataset indicates a value has been moved for analysis purposes. These values will be considered to be missing, and the planned statistical methodologies for coping with missing data will be applied for primary analysis. Supportive analysis will be done to evaluate with impact of this value on study conclusions.

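### SAP Sections 3 (attribute C), 5.4 and 8.4 list different intercurrent events for removing primary HbA1c values, and 5.4 leaves its list open-ended

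*SAP*

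**What the plan says.** **SAP 3, attribute C** gives as examples blood transfusion, prednisone treatment and "major modification in insulin regimen/doses outside the once recommended in the protocol". The values that follow are set to missing, and multiple imputation predicts what they would have been without the event.

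**SAP 5.4** lists blood transfusion, then "Use of concomitant treatments that are known to be associated with impact on HbA1c, specifically use of steroids", then "Shift change in work schedule from day worker to night worker or other life event that may affect HbA1c", which continues "such as any situation or major protocol deviation from the usual insulin doses outside of the ones specified in the protocol". A separate sentence says data from periods of InPen or pump failure cannot be interpreted. Censored data go to the missing-data methods.

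**SAP 8.4**, the operational section, refers to "intercurrent events such as blood transfusion or medical treatment with prednisone that would render subsequent values as not protocol-meaningful". The action is the same as in Section 3. Blind data review decides which values are affected, the values are kept in a supplementary dataset, and a supportive analysis examines their impact.

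**SAP 5.1** frames the scientific question around patients who do not need therapies "that would influence HbA1c measures (except for insulin"). Section 5.2 makes the same exception for the population. SAP 7.6.1 says all analyses follow the intent-to-treat principle.

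**SAP 2** says that under the alternative hypothesis "the modification of insulin for subjects on active treatment may be altered as a result of the co-administration of TTP399". It also sets the 0.3 non-inferiority margin that Evaluation 1 must meet before the study can be declared successful.

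**The concern.** These lists decide which observed HbA1c values enter the primary ANCOVA and which are replaced by imputed ones. A programmer working from 8.4 would keep HbA1c after a major insulin deviation. One working from Section 3 or 5.4 would remove it. Only 5.4 would remove it after a change of work shift or some other life event, and its wording sets no limit on what qualifies. The SAP does not define what makes an insulin modification major.

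The values feed the interval compared with 0.3 and the HbA1c superiority test. They may also reach the responder endpoint: SAP 7.5 imputes missing dichotomous outcomes as non-response, so a patient whose HbA1c improved could become a non-responder if a removed value counts as missing there. The SAP does not say whether it does.

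**Working it through.** **Step 1. The lists side by side**

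| | SAP 3, attribute C | SAP 5.4 | SAP 8.4 |
|---|---|---|---|
| Blood transfusion | yes | yes | yes |
| Steroids | prednisone | treatments affecting HbA1c, specifically steroids | prednisone |
| Major insulin change outside the protocol | yes | yes | not named |
| Shift change | not named | yes | not named |
| Other life event, any situation | not named | yes | not named |
| InPen or pump failure | not named | yes, in a separate sentence | not named |
| Form of the list | examples | bullets, the third open-ended | examples |
| Action | missing, then multiple imputation | censored data to missing-data methods | missing, then multiple imputation |

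Only transfusion and steroids are common to all three. Insulin deviation is in two sections. Shift change, life events and device failure are in one. Section 5.4 does not say whether its device-failure sentence reaches HbA1c or only device data; SAP 8.2 separately drops insulin data from pump-failure days.

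**Step 2. What the review can see.** SAP 8.4 makes the review blind to treatment. SAP 8.2 sends any HbA1c change above 1% in either direction to query, lets blind review judge whether the value suits the primary estimand, and imputes what is judged unusable. The outcome itself can therefore trigger review. If the planning SD of 1% (SAP 1.9) applies to change, and change is normal with mean zero (assumptions), the share queried is 2 × (1 − Φ(1)) = 32%.

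**Step 3. Size, as illustration only.** The documents give no rate for any of these events, so there is no plan figure to reproduce. Let d be the difference between arms in the share of HbA1c values removed, and e the average gap between the observed values and those imputed in their place, taken as equal in both arms.

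Shift in arm difference = d × e

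With d = 0.10 (assumed):

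- e = 0.2: 0.10 × 0.2 = 0.02; 0.02 / 0.3 = 7% of the margin
- e = 0.4: 0.10 × 0.4 = 0.04; 0.04 / 0.3 = 13%
- e = 0.8: 0.10 × 0.8 = 0.08; 0.08 / 0.3 = 27%

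Wider assumptions, d from 0.05 to 0.20 and e from 0.3 to 1.0, give 0.05 × 0.3 = 0.015 up to 0.20 × 1.0 = 0.20, or 5% to 67% of the margin. The sign reverses if the other arm has more removals.

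**Step 4. Against sampling error.** With SD 1% (SAP 1.9) and 45 per arm (SAP Table 1), before covariate adjustment, SE = 1 × √(2/45) = 0.21 and the 95% half-width is 1.96 × 0.21 = 0.41. A shift of 0.04 is 0.04 / 0.21 = 0.19 of a standard error. Non-inferiority would need an estimated difference (TTP399 minus placebo) below 0.30 − 0.41 = −0.11. A shift of 0.02 to 0.08 changes that conclusion only if the estimate lies within that distance of the boundary.

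**The case against.** The strongest reply is that the lists in Section 3 and 8.4 are introduced as examples, so they are incomplete definitions and not contradictory closed sets. That is fair, but it leaves the set of removed values undefined, which is the problem. It also does not explain why the operational section omits insulin.

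A reader might infer that treatment drives the insulin events and that removing values after them must therefore be informative. The documents do not show this. The sentence in SAP 2 concerns insulin modification in general, which Protocol 8.11 directs for everyone. The events in Section 3 and 5.4 are major departures from that guidance. Differing rates by arm are possible but not documented. Nothing ties a change of work shift to treatment; the objection there is vagueness.

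A reader might also infer that values are picked with the treatment arm in view, or that removal favours TTP399. Neither is supported. The review is blind to arm, and the direction depends on rates the documents do not give.

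The insulin exception in 5.1 and 5.2 can be read narrowly: all patients use insulin, so it cannot count as a prohibited concomitant therapy, while a major deviation might still be an intercurrent event. That reading is available, which is why the sections need reconciling and are not simply in contradiction.

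Finally, imputing as if the event had not happened is a legitimate estimand choice. Analyses with the removed values are planned (SAP 3, 8.2, 8.4), as is an observed-cases analysis with no exclusions (7.6.1). Keeping HbA1c after off-protocol insulin increases could also hide inferiority of TTP399. These points stand. They mean the insulin element has a real cost on either side, but they do not settle which values the primary analysis uses.

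**Conclusion.** The concern holds as an inconsistency in how the primary dataset is defined. Three sections give three lists, one of them open-ended, and the primary non-inferiority and superiority results use whichever values survive. The insulin element is unresolved within the SAP: it is included in Section 3 and 5.4, absent from 8.4, and in tension with 5.1, 5.2 and the intent-to-treat statement in 7.6.1. Blinding and the supportive analyses reduce the risk but do not remove it, because events can occur at different rates by arm and the primary decision still rests on imputed values.

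Size and direction cannot be known from the documents. The 0.02 to 0.08 range rests on an assumed 10-point difference in removal rates and an assumed gap of 0.2 to 0.8. It is small beside the sampling error and matters mainly for a result close to the margin. This should be corrected before unblinding; it does not show that the planned result is biased.

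**What to change.** 1. Put one identical closed list in SAP 3 (attribute C), 5.4 and 8.4: blood transfusion and systemic corticosteroids, the two items already common to all three. Replace the example wording so that the list is exhaustive.
2. Delete the life-event and any-situation wording from 5.4. Keep HbA1c observed after shift changes and life events in the primary analysis. State that the device-failure sentence does not remove HbA1c.
3. Reconcile major off-protocol insulin deviations with 5.1 and 5.2, and define major. To follow the insulin exception and intent-to-treat, keep the observed HbA1c in the primary analysis, make its exclusion a named sensitivity analysis, and report the 0.3-margin result both ways.

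The cost is SAP wording and one named analysis; SAP 3 and 8.4 already retain the moved values. There are two downsides. HbA1c variability may rise slightly. Retained values after off-protocol insulin increases could mask inferiority; the sensitivity analysis and the insulin-change comparison planned in SAP 2 address this, although the SAP calls that comparison nominal.
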